#### 9.6.3 Hyperuricemia Prophylaxis

Prior to beginning perifosine, all patients should be questioned about a history of hyperuricemia and/or gout. Patients with a known history of hyperuricemia and/or gout should receive prophylactic treatment with allopurinol 300 mg po daily. If severe gout does occur or uric acid levels increase, the dose of allopurinol should be increased at physician discretion.

#### 9.6.4 G-CSF Administration

Routine prophylactic use of G-CSF is not permitted. However, therapeutic use in patients with serious neutropenic complications, such as sepsis, may be considered at the investigator's discretion

#### 9.6.5 Other Concomitant Medications

Therapies considered necessary for the well being of the patient may be given at the discretion of the investigator. Other concomitant medications should be avoided except for analgesics, chronic treatments for concomitant medical conditions, or agents required for life-threatening medical problems. All concomitant medications must be recorded.

#### 9.6.6 Other Anticancer or Experimental Therapies

No other anticancer therapy (including chemotherapy, radiation, hormonal treatment or immunotherapy) of any kind is permitted during the study period.

## IRB#: 06-044 A(11)

No other drug under investigation may be used concomitantly with the study drug.

#### 9.6.7 Surgery

If neurosurgical management is required for reasons not due to tumor progression, these procedures must be documented, including the indications for surgery, the surgical operative note and pathology report.

9.6.8 Corticosteroids should be used in the smallest dose to control symptoms of cerebral edema and mass effect, and discontinued if possible.

Anti-seizure medications should be used as indicated. However, only patients not taking EIAEDs are eligible to enroll on this trial. Patients who were previously on a non-EIAED and need to change anticonvulsants should be started on another non-EIAED if at all possible. No delays in treatment would be required. Patients who were previously on no anticonvulsants should be treated with non-EIAEDs if at all possible. If for unavoidable clinical reasons (severe allergies, toxicities etc.) a patient is started on an EIAED, he/she should immediately be started on another non-EIAED and the EIAED should be tapered and discontinued as quickly as possible. The patient may continue the current treatment dose while a non-EIAED is re-started because an EIAED will likely increase metabolism of perifosine, reducing rather than increasing any potential anti-tumor effect and therefore any efficacy bias introduced would be negative rather than positive.

Patients who were previously on a non-EIAED and need to permanently change anticonvulsant, but who cannot change to another non-EIAED may continue the current treatment dose for the next 2 weeks while an EIAED is started. FOLLOWING THIS PERIOD, THE SUBSEQUENT TREATMENT DOSE MUST BE DISCUSSED WITH THE PI OR CO-PI. Treatment may be allowed to continue if the patient is felt to be deriving clinical benefit. In some cases this dose may be higher than the previously used dose.

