## **OBJECTIVES AND SCIENTIFIC AIMS**

- Primary aim:
  - Determine the efficacy of perifosine in patients with recurrent/progressive GBMs not taking EIAEDs as measured by 6mPFS.
- Secondary aims
  - Determine molecular effects of perifosine on AKT, RAS, and proliferation in malignant gliomas by analysis of resected tissue in patients on the surgical substudy.
  - Determine metabolic effects of perifosine on malignant gliomas by PET imaging.
  - o Identify molecular features that predict perifosine response.

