# IRB#: 06-044 A(11)

given at 6 hour intervals. Patients received dexamethasone and dolasetron mesylate prior to each dose during the loading period with lorazepam and prochlorperazine prn. Reported severe toxicities for this trial include anorexia, fatigue, dehydration, nausea/vomiting, constipation, diarrhea, elevated liver function tests, and decreased hemoglobin. The MTD and recommended phase II dose for this schedule was 900 mg loading dose (divided into 6 equal doses of 150 mg taken with food q 6 hourly) followed by 100 mg daily maintenance. Among 14 patients treated at the MTD, there were 4 grade 3 events (fatigue in 2 patients, nausea in 1 and vomiting in 1 patient). Subsequently a review of the pharmacokinetics for this study revealed that there was only a minimal increase in plasma concentration between dose level 3 and dose level 4. For this reason the actual doses used in subsequent phase II studies were a loading dose of 600 mg (150 x 4) and a maintenance dose of 100 mg. Among the 12 patients treated at dose level 2 there were 3 patients who experienced grade 3 fatigue and 1 patient with grade 3 nausea. There were no additional grade 3 toxicities recorded as probably due to the drug.

The gastrointestinal toxicities experienced on this protocol are summarized in the following table:

Table 6

NCI Trial II - A Phase I Trial of Perifosine with Different Loading/Maintenance Doses using the "Continuous Schedule" in Patients with Advanced Cancer

			]	Maximum intensity (CTC grade) during any treatment										
Dose	Dosage - Cycle	Patients		course										
Level	1	Treated		Na	usea			Von	niting			Dia	rrhea	
	(Loading /													
	Maintenance)		0	Ι	II	III	0	Ι	II	III	0	Ι	II	III
Ι	400 mg/50 mg	3		3								3		
II	600 mg/50 mg	7		3	3			3	2			3	1	1
	600 mg/100 mg	12		6	2	1		3	2			6	3	
IV	900 mg/100 mg	14		7	3	1		3	2	1		3	3	
V	900 mg/150 mg	6		4	1			4	0			2	3	

Patient diagnoses included pancreatic carcinoma (1 patient), sarcoma (5), colorectal carcinoma (19), ovarian carcinoma (2), renal cell (6), lung cancer (4), esophageal carcinoma (1), breast (1), cervical (1), glioblastoma (1) and tonsilar (1). One partial response in a patient with uterine sarcoma was reported. The responder received 18 cycles of therapy on study and has since been followed for 17 months without significant progression. Seven patients

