# IRB#: 06-044 A(11)

Enzyme activities associated with CYPIA2 (7-ethoxyresorufin 0-deethylation), CYP2B6 (S-mephenytoin Ndemethylation), CYP2C9 (tolbutamide methyl-hydroxylation), CYP2D6 (dextromethorphan 0-demethylation), and CYPZEI (chlorzoxazone 6-hydroxylation) were not inhibited by perifosine at any of the concentrations ( $0.25 - 100 \mu M$ ).

Perifosine	Percentage of Activity Remaining							
Conc	CYP1A2	CYP2A6	CYP2B6	CYP2C9	CYP2C19	CYP2D6	CYP2E1	CYP3A4/5
(µM)								
0.0	100.0	100.0	100.0	100.0	100.0	100.0	100.0	100.0
0.25	96.4	97.7	100.1	101.3	98.4	96.0	99.8	102.2
1	101.2	101.2	100.7	96.6	96.8	94.1	100.4	101.3
5	100.8	90.8	100.1	95.7	102.0	98.5	95.8	103.0
10	98.8	94.7	98.0	95.3	97.6	95.9	95.0	97.0
25	99.9	88.9	100.8	96.0	103.1	98.5	96.5	94.5
50	97.8	88.7	101.0	95.8	113.9	94.3	89.1	98.4
100	113.6	46.1	99.9	98.0	106.4	88.1	86.0	71.3

Table 10: The Effect of Perifosine on CYP1A2, CYP2A6, CYP2B6, CYP2C9, CYP2C19, CYP2D6, CYP2E1 AND CYP3SA4/5 Activities in Pooled Human Liver Microsomes

These data suggest that patients taking EIAEDs may have increased drug metabolism and a higher MTD than patients who are not taking EIAEDs. Therefore, to avoid the possibility of effects of EIAEDs on the metabolism of perifosine, and vice-versa, only patients not taking EIAEDs will be eligible for this trial as has become common in trials of novel agents for malignant glioma. (See Appendix 20.2 for a list of EIAED drugs).

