# 6.2 Subject Exclusion Criteria

- Patients must not be taking EIAEDs. If patients were previously on EIAEDs that have been discontinued, patients must have been off the agent for at least 2 weeks prior to registration.
- Patients must not have any significant medical illnesses or other history that in the investigator's opinion cannot be adequately controlled with appropriate therapy or would compromise the patient's ability to tolerate this therapy.
- Patients with a history of any other cancer (except non-melanoma skin cancer or carcinoma in-situ of the cervix), unless in complete remission and off of all therapy for that disease for a minimum of 3 years are ineligible.
- Patients must not have active infection or serious intercurrent medical illness.
- HIV-Positive patients receiving combination anti-retroviral therapy are excluded from the study due to possible retro-viral drug interactions.
- Patients must not have any disease that will obscure toxicity or dangerously alter drug metabolism.
- Surgical arm only: Patients must not have received prior therapy with signal transduction inhibitors (including but not limited to ZD1839/gefitinib/Iressa, OSI-774/erlotinib/Tarceva, rapamycin/sirolimus, CCI-779/temsirolimus, STI-571/imatinib/Gleevec, bevacizumab/Avastin, VEGF-Trap, AZD2171, sorafinib, sunitinib). Any questions about the eligibility based on prior treatments should be discussed with the PI or co-PI.

[figure not shown]

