## 9.2 Dosing

Perifosine will be given as a 600 mg loading dose on day 1. The loading dose will be divided into 4 equal doses of 150 mg each. The first 3 doses should be given with food in the adult day hospital to allow intravenous antiemetic prophylaxis, and 4th dose at bedtime at home. The interval between doses of perifosine should be no less than 4 hours. On day 2, patients will start the maintenance dose of 100 mg daily at bedtime at home.

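### Section 9.6.8 allows a raised perifosine dose with no stated limit for a patient who must stay on an EIAED; the cited enzyme data do not support it, and the analysis plan says nothing about such patients.

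*Combined protocol and SAP*

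**What the plan says.** **Population.** The primary aim (Section 2) is: "Determine the efficacy of perifosine in patients with recurrent/progressive GBMs not taking EIAEDs as measured by 6mPFS". The exclusion criteria state "Patients must not be taking EIAEDs", and Section 3.6 gives the reason: to keep EIAEDs and perifosine from affecting each other's metabolism.

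**Regimen.** Section 9.2 sets a 600 mg load on day 1, then: "On day 2, patients will start the maintenance dose of 100 mg daily at bedtime at home". Section 9.4, on perifosine-related adverse events, contains holds, reductions and a reduced re-load.

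**EIAED started on study.** The anti-seizure text in Section 9.6.8 treats two cases.

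- *Temporary EIAED.* The patient stays on the current dose while the EIAED is withdrawn. The justification is that induction would lower exposure, so "any efficacy bias introduced would be negative rather than positive".
- *Permanent EIAED, no alternative available.* The current dose continues for two weeks. The subsequent dose must then be discussed with the PI or co-PI, and treatment may go on if the patient seems to benefit. The paragraph ends: "In some cases this dose may be higher than the previously used dose". It gives no ceiling, step size or drug-level check.

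**Pharmacological basis.** After Table 10, Section 3.6 concludes: "These data suggest that patients taking EIAEDs may have increased drug metabolism and a higher MTD than patients who are not taking EIAEDs".

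**Reported MTD.** For the continuous schedule, Section 3.5.2 says "The MTD and recommended phase II dose for this schedule was 900 mg loading dose", followed by 100 mg daily maintenance.

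**Analysis.** Section 14 has no rule for GBM patients who start an EIAED or receive a raised dose.

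**The concern.** The increase in Section 9.6.8 has no numerical bound, while the trial's maintenance dose already equals that of the MTD reported for the same type of schedule. The only perifosine-specific data offered for a higher tolerable dose come from an experiment that did not ask that question.

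Two things are at stake. The first is safety: a patient could receive a maintenance dose above a reported MTD on an untested assumption about clearance. The second is interpretation: a GBM patient on a long-term EIAED and a non-protocol dose would, by default, be counted in an endpoint whose aim concerns patients not taking EIAEDs. The decision rule uses small counts, and nothing in the plan tells a reader how to see whether such patients influenced the result.

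**Working it through.** **1. The plan's own design figure.** Section 14: 12 GBM patients in stage 1, continue with at least 1 success; 37 in total, positive with at least 4; rates 5% and 20%.

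P(positive | p) = Σ over x ≥ 1 of P(Bin(12, p) = x) × P(Bin(25, p) ≥ 4 − x)

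- p = 0.20: 0.9024 (stated: at least 0.90).
- p = 0.05: 0.0935, so P(negative) = 0.9065 (stated: 0.90).

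The design reproduces and is not in question.

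**2. Dose figures side by side.**

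| Source | Schedule | Reported figure |
|---|---|---|
| Section 9.2 (this trial) | continuous | 600 mg load, 100 mg daily |
| Section 3.5.2, continuous | no scheduled break | MTD 900 mg load, 100 mg daily |
| Section 3.5.2, intermittent | load on day 1, then 20 days, 28-day cycle | MTD 900/150 mg in cycle 1, 300/150 mg later |
| Section 3.5.1, study D-21266-3079 | 21 of 28 days | MTD 200 mg daily |

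Section 9.1 defines this trial's dosing as continuous, so the second row is the like-for-like schedule. Its maintenance dose equals this trial's: 100 mg. Tablets are 50 mg (Section 5) and are kept whole unless a gastrostomy tube is used (Section 9.6.1). The smallest whole-tablet step from 100 mg is therefore 50/100 = 50%. In Table 6 the only level with maintenance above 100 mg is 900/150 mg, with 6 patients.

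The comparison concerns maintenance only, since this trial's load (600 mg) is below 900 mg. It applies to a patient still on 100 mg; a patient reduced to 50 mg under Section 9.4 could be raised without passing 100 mg.

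**3. What Table 10 measures.** Human liver microsomes were incubated with probe substrates and increasing perifosine concentrations, and remaining enzyme activity was recorded. At 100 µM, CYP3A4/5 activity was 71.3%, so inhibition was 100 − 71.3 = 28.7%, matching the 29% in the text. This is perifosine acting on the enzymes. The assay does not test whether the enzymes metabolize perifosine, or whether EIAEDs speed its clearance. Section 3.6 calls perifosine only a potential substrate, and Section 5 lists no reported drug interactions. A higher MTD with EIAEDs may be a reasonable hypothesis, but it does not follow from this table.

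**4. Drug-level sampling.** Section 9.3 and Appendix 20.4 schedule samples at baseline and weekly in weeks 2–4, plus surgery for the surgical arm. None is tied to starting an EIAED or changing dose.

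**5. Bias.** The negative-bias sentence needs an unchanged dose and increased metabolism. With a raised dose and unproven induction, exposure could be lower than, equal to or higher than that of other patients. The direction is unknown.

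**6. How far a few patients could move the error rate (illustration only).** The documents give neither the number k of affected patients nor their success probability q, so both are assumed. With k of the 25 stage-2 patients at q and all others at 5%, P(positive) is:

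| k | q = 0 | q = 0.05 | q = 0.20 | q = 0.40 |
|---|---|---|---|---|
| 1 | 0.088 | 0.093 | 0.111 | 0.135 |
| 3 | 0.076 | 0.093 | 0.149 | 0.228 |

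The result falls on either side of 0.0935 depending on q.

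**The case against.** **The increase is restricted.** It needs a patient who cannot change to another non-EIAED, discussion with the PI or co-PI, and perceived benefit; Section 4.1 also asks for immediate notification. This stands. But none of these conditions is a limit on dose.

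**Safety follow-up continues.** The hold and reduction rules of Section 9.4 cover all patients, and diaries, examinations and laboratory tests go on. This stands: what is missing is an upper limit and a drug-level check, not safety monitoring. Section 9.4 also addresses drug-related adverse events, so its having reductions only is not in itself a contradiction of Section 9.6.8.

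**Other schedules report higher daily MTDs.** True, as the table shows. Those schedules have a break in each cycle, so they do not settle the question for continuous dosing. Equally, it would be wrong to say that any increase passes every MTD in the document.

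**EIAED use is an entry exclusion.** Keeping enrolled patients in the count after a later medication change is ordinary practice. This stands, and is why the remedy below leaves the primary count alone.

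**Stronger readings the text does not support.** A reader might infer that the protocol claims negative bias for raised doses. It does not; that sentence belongs to the temporary, unchanged-dose case. A reader might also infer that a dose above the study dose is expressly granted. The text refers to the previously used dose, and a dose above 100 mg is allowed only because no ceiling is given.

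**Conclusion.** The point holds in a limited form and is worth correcting. Section 9.6.8 permits an increase without a stated bound. For a patient on 100 mg daily, any increase would exceed the maintenance dose of the continuous-schedule MTD, by at least 50% in whole tablets. The Section 3.6 inference of a higher MTD does not follow from Table 10. The raised-dose case has no bias argument, and Section 14 does not mention these patients.

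The number affected is unknown and probably small. It would be tempting to conclude that the type I error is inflated, or that such patients should not count as successes. The documents support neither. The error rate moves up or down with inputs the plan does not give, and refusing to count a success because of a post-entry event would reclassify outcomes and could itself bias 6-month PFS downward. The two-stage design is sound as stated.

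The conclusion assumes that Section 14's silence means such patients remain in the primary count.

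**What to change.** 1. The sponsor should reconcile the increase in Section 9.6.8 with Sections 9.2 and 9.4 and with the continuous-schedule MTD in Section 3.5.2. Whether any increase is allowed, and on what terms, is a clinical decision; none is proposed here.
2. Correct Section 3.6 to say that Table 10 shows inhibition of CYP enzymes by perifosine only and does not establish a higher MTD with EIAEDs.
3. In Section 14, state that all enrolled GBM patients stay in the primary count. Prespecify a sensitivity report of 6-month PFS with and without patients who took a long-term EIAED or received more than the Section 9 dose.

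The cost is amendment wording and one extra table. Sample size and decision rule are unchanged.

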#### **10.0 EVALUATION DURING TREATMENT/INTERVENTION**

#### 10.1 Clinical

History and physical examination (including vital signs, weight and KPS) will be performed at each clinic visit. Patients will have a follow up physical exam 1 week after the patient starts treatment and every first week of each subsequent cycle (4 week period).

## IRB#: 06-044 A(11)

A diary should be completed by the patient each week to score duration and severity of gastrointestinal side effects. Patients will also maintain a weekly patient treatment diary to track doses of perifosine taken at home and return the diary to the clinic each week.

#### 10.2 Laboratory

A CBC with differential and serum chemistry will be performed 1 week after the patient starts treatment, and every first week of each subsequent cycle.

- Albumin
- Alkaline phosphatase
- Total bilirubin
- Bicarbonate
- BUN
- Calcium
- Chloride
- Creatinine
- Glucose
- LDH
- Phosphorus
- Potassium
- total protein
- SGOT [AST], SGPT [ALT]
- Sodium
- Uric acid
- Magnesium

Serum pregnancy test should be obtained within 72 hours prior to the initiation of therapy for women of childbearing potential.

#### 10.3 Imaging and Molecular Studies

Patients not on the surgical arm will undergo imaging evaluation with brain MRI (with MR Perfusion and MR spectroscopy if possible) at baseline and every 8 weeks Patients unable to undergo MRI will have CT scans. Patients will also undergo FDG-PET imaging of the brain (at MSKCC) at baseline and every 16 weeks (4 cycles) to assist with interpretation of MRI. Patients will also undergo a brain FDG-PET scan after 1-2 weeks of therapy at MSKCC to investigate potential metabolic effects of perifosine and to explore early FDG-PET as a predictor of response by clinical and radiographic evaluations performed later.

## IRB#: 06-044 A(11)

Patients on the surgical arm will undergo baseline imaging evaluation with brain MRI (with MR Perfusion and MR Spectroscopy if possible) and FDG-PET at MSKCC no more than 2 weeks before pre-operative perifosine. Patients on the surgical arm will also undergo a pre-operative FDG-PET at MSKCC following at least 5 days of perifosine and before surgery to correlate metabolic and tissue effects during treatment. After surgery, a brain MRI must also be performed no more than 2 weeks before initiation of post-operative perifosine. It is expected that in most cases, the post-operative MRI (performed within 96 hours after surgery) will suffice and function as the new baseline scan before initiation of post-operative perifosine. Patients unable to undergo MRI will have CT scans. FDG-PET does not need to be repeated post-operatively before re-initiating perifosine. Patients will then undergo brain MRI every 8 weeks (with MR Perfusion if possible) and brain FDG-PET every 16 weeks (4 cycles) at MSKCC to assist with interpretation of MRI.

Fifteen unstained paraffin slides and 100 mg of flash frozen tissue will be used to evaluate the effect of perifosine on PI3K/AKT and RAS/MAPK signaling, the effect on proliferation, and other molecular effects. In addition, 100 mg of flash frozen tissue and one tube of serum will be collected for pharmacokinetic analysis.

All patients: The brain MRI, MR Perfusion, MR Spectroscopy and FDG-PET scans will be used for clinical care and be billed to insurance/patient with the exception of the FDG-PET performed after 1-2 weeks of therapy which is research in nature. In addition, such scans will be used to determine effects of perifosine on tumor blood flow and metabolism.

If available, 15 unstained paraffin slides and flash frozen tissue will be obtained from the surgery closest to initiation of this clinical trial. These will be used to evaluate molecular markers that could predict glioma sensitivity to perifosine such as a PI3K/AKT activity, RAS/MAPK activity, proliferation rate, and somatic mutations of potential oncogenes or tumor suppressor genes in tumor cell DNA.

[name] and members of his laboratory will conduct analyses of baseline tumor tissue for abnormalities of the RAS, AKT, and other signal transduction cascades that may predict tumor sensitivity to perifosine. [name] will also conduct analyses of tissue resected during treatment with perifosine (surgical arm of the study) to determine the effects of perifosine on signaling.

[name], Pharm. D. at the University of Wisconsin will conduct PK and tissue drug concentration analyses. AOI Pharmaceuticals subcontracted [name] to perform such assays. Please see section 20.3 for instructions on shipping tissue/serum to [name].

## IRB#: 06-044 A(11)

(Remainder of this page intentionally left blank.)

	Pre- Study	Wk 1	Wk 2	Wk 3	Wk 4	Wk 5	Wk 6	Wk 7	Wk 8	Wk 9	Wk 10	Wk 11	Wk 12	Wk 13	Off Study c
Perifosine administration a		х	Х	Х	Х	х	Х	Х	Х	х	х	Х	х	Х	
Informed consent	X														
Demographics	Х														
Medical history	Х														
Concurrent meds	X														
Physical exam	X		Х			Х				Х				Xf	
Vital signs	Х		Х			Х				Х				$\mathbf{X}^{\mathrm{f}}$	
Height	Х														
Weight	Х		Х			Х				Х				Xf	
Performance status	Х		Х			Х				Х				Xf	
CBC (w/diff, plts f )	Х		Х			Х				X				Xf	
Serum chemistry b	X d		Х			Х				Х				X d	
Serum pregnancy e	Х														
Adverse event evaluation	х	Х	X								Х				
Patient Diaries	Х	Х	X								Х				
Tumor measurements	Х	Tumor measurements are repeated every 8 weeks. Documentation (radiological) must be provided for patients removed from study for progressive disease.							Xc						
a: Perifosine: Dose b: Albumin, alkalin total protein, SG c: Off-study evalua from study for th d: Assessments to c	e phospha OT [AST] tion. It is is reason.	itase, to  , SGPT prefera	tal bilin [ALT], ble that	ıbin, bic sodium two cor	, uric ac secutiv	cid, mag e measu	nesium. rements	taken t		-		-	-	-	

Within 72 hours prior to initiation of therapy for women of childbearing potential only. Assessments to continue at least every 4 weeks while patient is on study.

e: f:

